8. STATISTICAL/ANALYTIC ISSUES

8.1 Adjustment for Covariates

Analyses of the change from baseline in efficacy endpoints utilizing MMRM methodology will adjust for the baseline score of the parameter of interest as a continuous covariate in the model. As the randomization of the study is stratified by the baseline GCA classification factor (either ≤ 70 or > 70), MMRM analyses will also take into account the GCA strata as a classification factor. The baseline age group (either < 6 years or ≥ 6 years) is also a categorical covariate in the MMRM analysis.

8.2 Handling of Dropouts or Missing Data

For randomized patients who discontinue early from the study, their early EOS efficacy evaluations will be used for the next scheduled time point only if the EOS evaluation is performed within 45 days of the next scheduled visit. In general, no further imputation will be used for descriptive analyses, or for primary and secondary efficacy analyses utilizing MMRM methodology.

8.3 Interim Analyses and Data Monitoring

No formal interim analysis or interim statistical testing for treatment comparisons is planned.

Patient safety data only in this study will be monitored by an independent DMC until the last patient completes his last scheduled study visit/assessment. The DMC will be an external group overseeing the safety of the study treatment, including both the investigational product and the IDDD, and will operate according to a charter determining the scope of its activities and frequency of meetings.

8.4 Multi-center Studies

This is a multicenter study utilizing a central randomization. The randomization is not stratified by center. It is planned that the data from all centers that participate in this protocol will be combined so that an adequate number of patients will be available for analysis. Because of the potential for a relatively large number of centers, and small numbers of patients at some centers, no subset analyses by center are planned. No adjustment for center effect will be utilized in the statistical analyses.

8.5 Multiple Comparisons/Multiplicity

The family-wise type I error rate (FWER) for the statistical tests of the primary, key secondary and other selected secondary efficacy endpoints (specified below) will be controlled at 0.05. To strongly control the FWER at this level, a Gate-keeping approach will be utilized in which each family of statistical tests will be conducted in a sequential manner. The test for the primary endpoint will be conducted first at the 5% significance level and, if significant, the key secondary endpoint will be similarly tested at the 5% significance level. If these two tests are

both significant, test of the additional secondary efficacy endpoints specified below will be conducted using the Hommel closed testing procedure (1988) to control the FWER.

The hypotheses for the primary, key secondary and other selected secondary efficacy endpoints will therefore be grouped into 3 ordered Gatekeeper families defined as follows:

[figure not shown]
- Family 1 (F1): Hypothesis test for the primary endpoint
- Family 2 (F2): Hypothesis test for the key secondary endpoint
- Family 3 (F3): Hypothesis tests for the change from baseline to Visit Week 52 for the following 6 endpoints:
 - Verbal, Nonverbal and Spatial standard scores from the DAS-II;
 - Communication, Daily Living Skills and Socialization standard scores from the VABS-II;

The 3 sets of hypotheses in F1, F2 and F3 will be tested sequentially, with F1 and F2 serving as serial gatekeepers. The null hypothesis of no treatment difference for the primary endpoint will be tested first in F1. The statistical test for the key secondary endpoint in F2 may only be declared statistically significant if a significant result is also achieved for the primary efficacy endpoint. Since F1 and F2 each contain a single null hypothesis to be tested, each of the two tests will be conducted at the 5% significance level.

Further, only if the null hypotheses for both the primary and key secondary endpoints are rejected in F1 and F2, can any of the tests for the endpoints specified in F3 be declared statistically significant. If statistical significance is obtained for the hypothesis tests in F1 and F2, the Hommel (1988) closed testing procedure will be used to control the FWER within F3, with each hypothesis test in F3 equally weighted. In this case, SAS Proc MULTTEST will be used to calculate and report adjusted p-values for each endpoint in F3.

The sample SAS code is presented in the [appendix 9.2.6](#).

The multiplicity adjustment for the primary and secondary endpoints is shown in the following flowchart:

All other endpoints not included in F1, F2 or F3 above are considered supportive and any statistical tests comparing treatments will be made without adjustment for multiplicity. The resulting p-values from these supportive analyses will be interpreted descriptively as summarizing the weight of evidence for a treatment difference and may suggest avenues for further exploratory analyses or generate formal hypotheses to be tested in future trials.

8.6 Examination of Subgroups and Interactions

Please see section 6.7.4 for a description of subgroup analyses and tests for interaction.

8.7 Sensitivity Analyses

Sensitivity analyses for the primary and key secondary endpoints will be conducted to assess missing data assumptions in the MMRM analyses (Siddiqui et al. 2009). The sensitivity analyses below will use worst-observation-carried forward (WOCF) to impute missing data at the Visit Week 52 time point. Within a given patient, the worst (lowest) observed score prior to Visit Week 52 (including the baseline value) will be used for the imputation of their missing Visit Week 52 value.

The first sensitivity analysis will compare the treatment groups at the Visit Week 52 time point using an analysis of covariance model with WOCF (ANCOVA-WOCF). The ANCOVA-WOCF model will include fixed categorical effects for treatment, baseline GCA classification factor (either ≤ 70 vs. > 70), baseline age group (either < 6 years or ≥ 6 years), and the corresponding baseline score as a continuous covariate. The sample SAS code is presented in appendix 9.2.7. The treatment difference in least squares means, 95% confidence interval and p-value from the ANCOVA-WOCF model will be compared to the corresponding inferential statistics at Visit Week 52 from the primary or key secondary MMRM model.

The second sensitivity analysis, the van Elteren (vE) test with WOCF (vE-WOCF) will be used to compare treatment groups at Visit Week 52. This test is based on the ranked changes from baseline after imputation of the Visit Week 52 value using WOCF. Baseline age group (either < 6

years or ≥ 6 years) and baseline GCA score (either ≤ 70 or > 70) will be used as stratification factors in the van Elteren test. The sample SAS code is presented in [appendix 9.2.7](#).

If the primary or key secondary endpoint is missing in $> 15\%$ of patients in either treatment group, then an MNAR pattern mixture model (PMM) will be fit with control-based multiple imputation, according to the sequential imputation method described by Ratitch and O'Kelly (2011). Five hundred complete datasets will be imputed and the analysis of each imputed dataset will compare the treatment groups at the Visit Week 52 time point using an analysis of covariance (ANCOVA) model. The ANCOVA model will include fixed categorical effects for treatment, baseline GCA classification factor (either ≤ 70 vs. > 70), baseline age group (either < 6 years or ≥ 6 years), and the corresponding baseline score as a continuous covariate. The least squares mean difference estimates will be averaged and the associated SEs will be summarized based on within-imputation and between-imputation variance using the SAS MIANALYZE procedure to yield a final estimate with associated 95% CI and p-value. The sample SAS code is presented in [appendix 9.2.8](#).

If the MMRM model for the primary or key secondary endpoint fails to converge using an unstructured covariance matrix, an AR(1) covariance structure will be used. In this case, additional covariance structures will be tried as sensitivity analyses to assess the robustness of the results, including compound symmetric and Toeplitz structures.

If there are cases in which subjects receive a study treatment that differs from the treatment to which they were randomly assigned, MMRM, ANCOVA-WOCF and WRS-WOCF analyses of the primary and key secondary endpoints will be performed by treatment actually received.

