6.7.1 Primary Analysis

For the pivotal study, the primary efficacy endpoint is the change from study baseline (Screening Visit) to Visit Week 52 in the General Conceptual Ability (GCA) score as measured by the DAS-II. The primary analysis will compare the treatment groups using a linear mixed model repeated measures (MMRM) analysis (Malinckrodt et al. 2008; Siddiqui et al. 2009). The repeated measures are the change from baseline GCA score obtained at the scheduled Visit Weeks 16, 28, 40, and 52, respectively. The model will include fixed categorical effects for treatment, visit week, treatment by visit week interaction, baseline GCA classification factor (either ≤ 70 or > 70), baseline age group (either < 6 years or ≥ 6 years), treatment by baseline GCA classification factor interaction, treatment by baseline age group interaction, interaction between baseline GCA classification factor and baseline age group, genotype, and the baseline GCA score as a continuous covariate. Visit week is defined as nominal visits, unless specified otherwise.

SAS Proc Mixed with restricted maximum likelihood estimation (REML) and an unstructured within-patient covariance structure will be used. If this model fails to converge, a first order autoregressive (AR(1)) covariance structure will be used for the primary analysis. Due to small sample size of ITT Population with baseline age ≥ 6 years, MMRM model may fail to converge when low count of subjects with baseline age ≥ 6 years exists in either treatment group. If this model fails to converge, the treatment by baseline age group interaction and /or interaction between baseline GCA classification factor and baseline age group will be removed from the model. The Kenward-Roger approximation will be used to estimate denominator degrees of freedom for tests of fixed effects. The assumptions of the model, including normality, will be evaluated using residual and other diagnostic plots of model fit.

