6.7.2 Key Secondary Analysis

The key secondary efficacy endpoint is the change from study baseline (Screening Visit) to Visit Week 52 in the Adaptive Behavior Composite (ABC) score as measured by the VABS-II. The key secondary analysis will compare the treatment groups using a linear mixed model repeated measures (MMRM) analysis. The repeated measures are the change from baseline ABC scores obtained at the scheduled Visit Weeks 16, 28, 40, and 52, respectively. The model will include fixed categorical effects for treatment, visit week, treatment by visit week interaction, baseline GCA classification factor (either ≤ 70 or >70), baseline age group (either <6 years or ≥ 6 years),

treatment by baseline GCA classification factor interaction, treatment by baseline age group interaction, interaction between baseline GCA classification factor and baseline age group, genotype, and the baseline ABC score as a continuous covariate.

SAS Proc Mixed with restricted maximum likelihood estimation (REML) and an unstructured within-patient covariance structure will be used. If this model fails to converge, a first order autoregressive (AR(1)) covariance structure will be used instead. The Kenward-Roger approximation will be used to estimate denominator degrees of freedom for tests of fixed effects. The assumptions of the model, including normality, will be evaluated using residual and other diagnostic plots of model fit.

From this model, least squares means, standard errors, treatment differences in least squares means, and 95% confidence intervals will be estimated for each time point. The significance test will be based on the treatment comparison of least squares means at Visit Week 52 from this model, and a p-value will be presented for this time point only. Estimated least squares means for change from baseline and the observed absolute values (\pm SE) by treatment group will be plotted over time.

The sample SAS code is presented in [appendix 9.2.2](#).

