9.2.1 Sample SAS code for the primary analysis

```
ods output estimates=est Tests3=FixF;
ods graphics on;
proc mixed data=adef data=adef covtest;
  class Trt VisitWk GCAclass Agegroup Genotype usubjid;
  model GCAchgBL = GCAclass Trt VisitWk Trt*Visitwk GCABL Agegroup Trt*GCAclass
  Trt*Agegroup GCAclass* Agegroup Genotype / ddfm=KR residual;
  repeated VisitWk / type=un subject=usubjid rcorr;
  estimate "Trt diff at Week 16" Trt 1 -1 Trt*VisitWk 1 0 0 0 -1 0 0 0 / cl;
  estimate "Trt diff at Week 28" Trt 1 -1 Trt*VisitWk 0 1 0 0 0 -1 0 0 / cl;
  estimate "Trt diff at Week 40" Trt 1 -1 Trt*VisitWk 0 0 1 0 0 0 -1 0 / cl;
  estimate "Trt diff at Week 52" Trt 1 -1 Trt*VisitWk 0 0 0 1 0 0 0 -1 / cl;
  lsmeans Trt*VisitWk / cl;
run;
```

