9.2.7 Sample SAS code for sensitivity analysis using WOCF

- ANCOVA-WOCF

```
proc mixed data=adefwocf;  
  class GCAclass Agegroup Trt;  
  model GCAchgBL = GCAclass Agegroup Trt GCABL AgeBL;  
  estimate "Diff. at month 13" Trt 1 -1/cl;  
  lsmeans Trt /cl;  
  ods output Estimates=E_ANCOVA;  
  where VisitWk=52;  
run;
```

- vE-WOCF;

```
proc npar1way data=adefwocf ;  
  strata Agegroup GCAclass;  
  class Trt;  
  var GCAchgBL;  
  where VisitWk=52;  
run;
```

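### The comparison of ANCOVA-WOCF with the primary MMRM changes the mean model together with the imputation, and no bridging fit separates the two

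*SAP*

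**What the plan says.** SAP 8.7 states that the sensitivity analyses for the primary and key secondary endpoints "will be conducted to assess missing data assumptions in the MMRM analyses". SAP 9.3.6 gives the same purpose and names the missing-at-random assumption. For ANCOVA-WOCF, the planned use of the estimate, interval and p-value is stated: "ANCOVA-WOCF model will be compared to the corresponding inferential statistics at Visit Week 52 from the primary or key secondary MMRM model".

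The mean models on the two sides are:

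- **Primary MMRM (SAP 6.7.1).** Besides treatment, visit, treatment-by-visit, GCA class and age group, it has "treatment by baseline GCA classification factor interaction, treatment by baseline age group interaction", then "interaction between baseline GCA classification factor and baseline age group, genotype, and the baseline GCA score as a continuous covariate". The code in 9.2.1 agrees: "Trt*Agegroup GCAclass* Agegroup Genotype / ddfm=KR residual".
- **Key secondary MMRM (SAP 6.7.2).** The same structure with baseline ABC: "treatment by baseline GCA classification factor interaction, treatment by baseline age group interaction, interaction between baseline GCA classification factor and baseline age group", plus genotype.
- **ANCOVA-WOCF (SAP 8.7).** Treatment, GCA class, age group and baseline score only.
- **ANCOVA step of the pattern mixture model (SAP 8.7).** The same short list: "The ANCOVA model will include fixed categorical effects for treatment, baseline GCA classification factor", age group and baseline score. It runs only if more than 15% of patients in an arm lack the endpoint.
- **Sample code for both ANCOVAs (9.2.7, 9.2.8).** A continuous age term is added, as in "model GCAchgBL = GCAclass Agegroup Trt GCABL AgeBL". Neither the 8.7 text nor the MMRM has it.

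In Protocol 10.5.1 and 10.8.6 the baseline covariates of the two models matched: GCA class and baseline score. The SAP enlarged the MMRM but added only age group to ANCOVA-WOCF.

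**The concern.** A missing-data sensitivity analysis is informative when the missing-data assumption is the main thing that changes. Here the set of fixed effects changes as well.

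The weighting changes with it. With treatment-by-age and treatment-by-GCA class in the model, the LS-means contrast in 9.2.1 averages the subgroups equally. The main-effects ANCOVA has one treatment coefficient, in which a small age group counts roughly in line with its size. For 4 to 10 patients out of 48 that share is 4/48 = 8% to 10/48 = 21%, against 50% in the MMRM contrast.

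A gap could then be taken as fragility to missing data when it comes from the model. Close agreement could equally hide two differences that cancel. The SAP plans no fit that tells these apart.

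**Working it through.** **1. Planning figure.** Inputs from SAP 4.2: difference 11, SD 11.6, 32:16, two-sided 0.05, 10% missing.

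- Patients left: 28.8 and 14.4.
- SE = 11.6 × √(1/28.8 + 1/14.4) = 3.74; noncentrality = 11/3.74 = 2.94.
- Noncentral-t power: 81.8% (81.2% at 29:14). The stated 80% is reproduced, so 11 and 11.6 are used below.

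**2. What the SAP's own simulation covers.** SAP 9.3.4.1 reports near-identical Month 13 estimates on complete data: 11.013 (MMRM) and 11.016 (ANCOVA). By 9.3.2, those two models had matched covariates and no genotype or baseline interactions. That agreement does not carry over to the pair now planned.

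**3. The planned pair on complete data.** Simulation inputs:

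- From the documents: Appendix III means and AR(1) correlation 0.8, SDs set so that Week 52 has 11.6, and 32:16.
- Assumed: the number aged 6 or over (SAP 6.7.1 says only that it is small) and a five-category genotype mix at 10-35% each, unrelated to outcome.
- No value is missing, so any gap comes from the models.

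With a fixed number aged 6 or over and a homogeneous effect:

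| Aged ≥6 of 48 | Gap SD, SAP pair | Gap SD, all MMRM terms in the ANCOVA | SE of that ANCOVA |
|---|---|---|---|
| 4 | 2.4 | 7.1 | 8.1 |
| 6 | 1.9 | 5.6 | 6.7 |
| 10 | 1.4 | 3.8 | 5.3 |

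The SAP pair differs by more than 2 points in about 12-37% of trials. The SAP's ANCOVA has an SE of about 3.6. If the MMRM is refitted with the ANCOVA's covariates, the gap SD falls to 0.6-0.8.

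A second set of up to 800 trials per case fixed the expected share aged 6 or over instead:

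| Share ≥6; effect in ≥6 | Mean gap | Gap SD | Gap >2 points | Disagree on p<0.05 | Matched pair: gap SD; >2 points |
|---|---|---|---|---|---|
| 10%; same | -0.06 | 2.16 | 31% | 12% | 0.90; 4% |
| 15%; same | 0.07 | 1.88 | 26% | 11% | 0.91; 4% |
| 25%; same | 0.00 | 1.39 | 14% | 8% | 0.83; 4% |
| 10%; none | -0.37 | 2.11 | 31% | 18% | 0.96; 5% |
| 15%; none | -0.36 | 2.00 | 32% | 17% | 1.13; 9% |
| 25%; none | -0.37 | 1.74 | 24% | 15% | 1.35; 12% |

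Two cautions apply. Trials in which the full model was not estimable were skipped: 306 and 341 of 800 at a 10% share, 10 and 12 at 25%. This second set also used ten covariance updates and no Kenward-Roger correction, so its p-value column is approximate.

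**4. With the fallback.** SAP 6.7.1 lets both age interactions go if the primary MMRM does not converge. At a 15% share the gap SD is then 1.02 (more than 2 points in 6%) with a homogeneous effect, and 1.22 (11%) with none in patients aged 6 or over. That is close to the matched pair.

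**5. Size of the effect being looked for.** With about 20% drop-out, SAP Tables A7 and A9 separate MMRM from ANCOVA-LOCF by 11.051 - 9.389 = 1.66 and 10.682 - 9.106 = 1.58 points. Model noise with an SD of 1.4-2.4 is of the same order.

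**The case against.** **The short ANCOVA is a reasonable model.** This stands. In 9.2.1 the treatment-by-age and treatment-by-GCA class terms do not vary by visit, so the less variable early visits help to estimate them. A Week 52 ANCOVA has only Week 52 data for them. A reader might infer that the cure is to give both models identical fixed effects. The simulation shows the opposite: the ANCOVA's SE rises from about 3.6 to 5-8 points and the gap widens.

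**The gap is noise, not bias.** This largely stands. A reader might infer from the unequal weighting a systematic shift of several points. If the effect were 11 below age 6 and zero above, equal weighting at Week 52 alone would give 0.5 × 11 = 5.5. The MMRM does not behave that way, because its age interaction is held constant over visits. At a 15% share the mean estimates were 8.93 (MMRM) and 9.29 (ANCOVA), a gap of about -0.4. Even a matched pair disagrees somewhat.

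**The fallback may remove most of the difference.** It may, but only if the model fails to converge. Treatment-by-GCA class and genotype still differ after it, and 6.7.2 does not repeat it for the key secondary model.

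**Scope is limited.** The direct comparison is stated for ANCOVA-WOCF only. The pattern mixture model needs more than 15% missing in an arm, while planning allows up to about 10%. The rank test with WOCF cannot carry these terms and lies outside the point. The extra age term moved the gap SD by only about 0.1. All of this is accepted.

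**Conclusion.** The mismatch is explicit in text and code, and no planned analysis separates its effect from that of imputation. Its cost is extra disagreement between the sensitivity and primary estimates: an SD of about 1.4 to 2.4 points on complete data, and more than 2 points in about 12-37% of trials, assuming 4 to 10 of 48 patients aged 6 or over and the genotype mix above. With more such patients, or under the fallback, it is smaller.

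A reader might go further and say that no gap can be read as a missing-data effect, or that the primary result is in doubt. Neither is supported. The mean gap is near zero under a homogeneous effect, a large gap would still carry information, and the primary and key secondary p-values are not touched. This is an inexpensive improvement to a supportive analysis.

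**What to change.** Keep the Week 52 ANCOVA as specified in the 8.7 text and add a bridge there, for each of the two endpoints:

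- (a) the observed-data MMRM refitted with the ANCOVA's covariates: treatment, visit, treatment-by-visit, GCA class, age group and baseline score;
- (b) the same ANCOVA on observed Week 52 scores, without imputation.

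State that the missing-data effect is read from ANCOVA-WOCF, and the pattern mixture model if run, against (a) and (b), not against the primary MMRM directly. The step from the primary MMRM to (a) shows the change of model. The step from (b) to ANCOVA-WOCF shows the imputation, and is zero if nothing is missing.

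Make the continuous age term in 9.2.7 and 9.2.8 agree with the 8.7 text. Do not add the MMRM's interactions and genotype to the one-visit ANCOVA.

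The cost is two supportive fits per endpoint, a few lines of SAP text and code, and no new data.

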4.2 Determination of Sample Size/Randomization

Based on study HGT-HIT-050/045 Phase I/II data, the observed decline in mean General Conceptual Ability (GCA) standard score (SS) in No IT treatment patients was estimated to be 13.7 points with a standard deviation of 9.4 after 12 months. For the sample size calculation, we conservatively assumed an approximately 1 point per month rate of decline in the No IT treatment arm, so that the theoretical decline would be 13 points from baseline (Screening Visit) to Visit Week 52 (~ 13 months). As up to 2 months may elapse between the screening assessment and the start of idursulfase-IT treatment, a mean decline of 2 points at end of study would be expected if idursulfase was effective in stabilizing the decline. Therefore, in such a case, the mean projected treatment difference at Visit Week 52 would be 11 points, which is considered a clinically meaningful treatment difference.

Using a 2:1 allocation ratio, a sample size of 48 randomized patients (about 32 IT treated patients and 16 no IT treatment patients) will yield 80% power to detect a clinically meaningful mean treatment difference of 11 points in the primary endpoint, GCA change from baseline to Visit Week 52. This calculation further assumes a common standard deviation for the change from baseline of 11.6 points, a type-I error rate of 0.05 for a two-sided two-sample t-test, with approximately up to 10% missing an assessment at Visit Week 52. Given this sample size, and conditional on rejection of the null hypothesis for the primary endpoint, the power would be 80% to detect a clinically meaningful mean difference of 10 points in the key secondary endpoint, change from baseline in ABC standard score at Visit Week 52, assuming a standard deviation for the change from baseline of 10.5 points for a two-sided two-sample t-test with a significance level of 5% and 10% missing an assessment at Visit Week 52.

The variance estimate for this sample size was determined based on a blinded variability assessment (BVA) performed as specified in the prior protocol version (Amendment 3); refer to

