9.3.3 Missing data

Monotone missing data with differential drop-out by treatment after month 4 was generated using a logistic regression model for the probability of drop-out. Simulations with data missing at random (MAR) and missing not at random (MNAR) were performed. Under MAR, conditional on the variables in the model, the missing data depends on the observed outcomes, however, under MNAR, missing data depends on both observed and unobserved outcomes. For MAR data, the probability of drop-out at a particular time point was dependent on treatment and the observed score at the previous visit. For MNAR scenarios, the probability of missing data also depended on the current visit score, which was unobserved in the subsequent analysis. In both cases, the logistic model was specified such that worse scores (greater declines) resulted in a higher probability of missing data. An overall drop-out rate of approximately 20% was assumed, with higher drop-out in the control versus the active arm (approximately 30% versus 15%) under the alternative hypothesis and equal drop-out under the null hypothesis. No imputation for missing data was employed for the MMRM analysis. LOCF was used to impute missing data for the ANCOVA analysis (ANCOVA-LOCF). Note that LOCF and WOCF are expected to be very similar methods in these simulations and the results should apply to both methods since a mean monotonic decline in the control arm and a constant value after Month 4 in the active arm was assumed under the alternative hypothesis. A mean monotonic decline in both arms is assumed under the null hypothesis.

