9.3.5 Conclusions

The following conclusions can be made from these simulation results:

- In performing the MMRM analysis using an unstructured covariance structure across all sets of simulations, we encountered no model convergence problems despite the relatively limited sample size
- In the absence of missing data, MMRM returned the correct means and variances at each Month for data generated under both the null and alternative hypotheses and the estimates at Month 13 were nearly identical to ANCOVA
- In simulations with 20% MAR data (approximately 15% and 30% missing data in active and control arms respectively), the MMRM estimates of the mean (SE) treatment differences remained correct, while ANCOVA-LOCF produced estimates that were biased downward at the primary Month 13 time point
- In simulations with 20% MNAR data (approximately 15% and 30% missing data in active and control arms respectively), both the MMRM and ANCOVA-LOCF estimates of the mean (SE) treatment differences were biased downward, however the average ANCOVA-LOCF Month 13 estimate was substantially more biased, underestimating the true mean value by more than 15%
- For all missing data scenarios under the alternative hypothesis, statistical power was similar for MMRM and ANCOVA-LOCF (approximately 80-89%). This was true for MAR and MNAR data scenarios in part because ANCOVA-LOCF tended to underestimate both the true mean treatment difference and its standard error. For all missing data scenarios under the null hypothesis, type I error rates were similar for the two methods, and close to the expected 5% level, although MMRM demonstrated better control of type I error under MNAR data.

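### SAP 8.7 runs its only MNAR analysis above a 15% missing-data trigger; at the planned rate of about 10% it would more often than not be skipped, leaving only WOCF to test the MMRM assumption

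*SAP*

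**What the plan says.** SAP 8.7 introduces its sensitivity analyses for GCA and ABC as tests of the missing-data assumptions behind the MMRM. Two always run: an ANCOVA and a van Elteren test, both after WOCF imputation at Week 52. For WOCF, "the worst (lowest) observed score prior to Visit Week 52 (including the baseline value) will be used".

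A third analysis, the control-based pattern mixture model, is fitted only when the primary or key secondary endpoint is missing in more than 15% "of patients in either treatment group, then an MNAR pattern mixture model (PMM) will be fit with control-based multiple imputation". Sample code is in SAP 9.2.8. The other checks in SAP 8.7 (alternative covariance structures, analysis by treatment received) and the reduced-population MMRM in SAP 6.7.1 do not concern missing data.

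SAP 4.2 plans "a sample size of 48 randomized patients (about 32 IT treated patients and 16 no IT treatment patients"), "with approximately up to 10% missing an assessment at Visit Week 52".

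Appendix III compares MMRM with ANCOVA-LOCF by simulation. SAP 9.3.3 adds: "Note that LOCF and WOCF are expected to be very similar methods in these simulations". SAP 9.3.6 states that LOCF and WOCF both rest on MCAR, a stronger assumption than the MAR behind MMRM. The same section then names ANCOVA-WOCF among the analyses that will assess the MAR assumption.

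**The concern.** The sample-size rate lies below the trigger, so the analysis that departs from MAR may well not run. What remains is WOCF, which holds a patient who leaves at his lowest score to date. For an IT patient who was stable when last seen, that is roughly where MMRM under MAR would put him. If stopping treatment means resuming the decline of about 1 point a month that the SAP assumes for controls, neither method shows it. Agreement between WOCF and MMRM could then be read as support for MAR when it is no test of it.

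A patient with baseline only is a special case. WOCF gives him zero change, in either arm, in a disease assumed to lose 13 points by Week 52. The SAP no longer uses the Week 16 median imputation of Protocol 10.8.1 (SAP 8.2), so such a patient contributes no outcome to the MMRM either.

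At stake is how far a positive Week 52 result can be defended against the question of missing data, in an open-label trial where only one arm has surgery, an implant and monthly injections.

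**Working it through.** **1. The plan's own figures.**
- Sample size (SAP 4.2): the SAP says 48 patients "will yield 80% power to detect a clinically meaningful mean treatment difference of 11 points in the primary endpoint", with a "common standard deviation for the change from baseline of 11.6 points" and two-sided alpha of 0.05. A two-sample t-test at 2:1 needs 14 controls and 28 IT patients, 42 in all; 42 / 0.9 = 46.7, so 47 against the stated 48. Power at 28/14 evaluable is 80.7%. Reproduced.
- Simulated ANCOVA-LOCF bias (SAP Tables A7 and A9): 9.389/11 - 1 = -14.6% under MAR and 9.106/11 - 1 = -17.2% under MNAR. Reproduced.

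**2. What the trigger means in patients.**
- Control: 15% of 16 = 2.4. Two missing (12.5%) do not trigger; three (18.75%) do.
- IT: 15% of 32 = 4.8. Four missing (12.5%) do not trigger; five (15.6%) do.

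**3. How often it fires.** Assume independent patients, a 10% chance of a missing Week 52 score in each arm, and GCA and ABC missing together.
- P(at least 3 of 16) = 0.211; P(at least 5 of 32) = 0.211.
- P(either) = 1 - 0.789 x 0.789 = 0.378, so the analysis is skipped with probability 0.622.
- If the total is fixed and split at random, it fires with probability 0.316 at 5 of 48 missing and 0.101 at 4 of 48.
- At a true 5% rate it fires with probability 0.062.

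**4. What the skipped analysis could show.** Inputs are from SAP 9.3.2: IT means -2 at all four visits; control means -4, -7, -10, -13; variances 9, 25, 64, 100; AR(1) with correlation 0.8 (Table A1). Illustrative assumption: 4 of 32 IT patients (12.5%, just under the trigger) were last seen at -2 and no control is missing. MMRM under MAR expects -2 for them at Week 52. Control-based imputation expects -13 + (covariance with Month 13 / variance at last visit) x (-2 - control mean at last visit):

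| Last seen | Expected Week 52 change | Shift in difference |
|---|---|---|
| Month 4 | -13 + (15.36/9) x 2 = -9.6 | 7.59 x 4/32 = 0.95 |
| Month 7 | -13 + (32/25) x 5 = -6.6 | 4.6 x 4/32 = 0.58 |
| Month 10 | -13 + (64/64) x 8 = -5.0 | 3.0 x 4/32 = 0.38 |
| Baseline only | -13 | 11 x 4/32 = 1.38 |

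**5. What WOCF shows for the same patients.** If their lowest score is also -2, WOCF imputes -2 and the difference stays at 11. If they have baseline only, it imputes 0: the IT mean becomes (28 x -2 + 4 x 0)/32 = -1.75 and the difference 11.25. WOCF shows none of the shift in the first case and moves the other way in the second.

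**6. Scale.** With 28 and 16 evaluable and SD 11.6, the standard error of a simple difference is 11.6 x sqrt(1/28 + 1/16) = 3.6. The shifts are roughly 0.1 to 0.4 standard errors.

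**The case against.** Several points on the other side are sound.

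- A reader might infer that the control-based model never runs at 10% missing. It can: the rule applies to either arm and either endpoint, and step 3 gives about a 38% chance.
- A reader might carry the simulated 15% to 17% bias over to this setting. SAP 9.3.5 says "the average ANCOVA-LOCF Month 13 estimate was substantially more biased, underestimating the true mean value by more than 15" per cent, but under drop-out that left 27% to 29% of controls missing at Month 13, where the trigger would fire. At about 10% missing, with the SAP's means and drop-out assumed unrelated to outcome and spread evenly over Months 7, 10 and 13, the expected WOCF bias is about -7% to -9% (LOCF about -5% to -8%).
- That bias is downward. Carry-forward mainly flatters controls who leave, so it shrinks the difference when the drug works. The documents do not support a claim that WOCF generally favours IT; the direction depends on which arm loses patients.
- Counting baseline as a candidate worst score does not make WOCF lenient when later scores exist. It can only lower the imputed value or leave it unchanged. The difficulty is confined to baseline-only patients, whom Protocol 10.8.1 regards as unlikely and who may be in either arm.
- The 1.4-point figure is an extreme. The SAP's model conditions on observed visits, so the usual shift is under 1 point.
- Appendix III offers design-stage reassurance: under simulated MNAR drop-out, MMRM bias was about -3% and type I error 4.53%.

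The last point only goes so far. Those simulations drew every IT patient from the IT mean profile whether or not he left, so they never examine loss of benefit after stopping. None of these objections supplies an unconditional analysis that departs from MAR in that direction.

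**Conclusion.** The point stands as a modest gap in robustness. At the missing rate the plan itself expects, the only analysis able to test the MAR assumption against loss of benefit is more likely to be skipped than run (about 62%), and the difference between 2 and 3 missing controls can settle it. The WOCF analyses cannot take its place, on the SAP's own account of what they assume.

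The amount at issue is about 0.4 to 0.95 points of an 11-point effect for 4 of 32 IT patients last seen at -2, and up to 1.4 points if none of them has a post-baseline score. This rests on the SAP's simulated means and covariance, no missing controls, and IT patients following the control course after leaving. The 62% rests on a true 10% rate in both arms, independence, and both endpoints missing together; if GCA and ABC are missing in different patients, the trigger fires somewhat more often.

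The documents do not show that the primary result would be overturned or that the MMRM is the wrong primary analysis. A shift of this size would matter only for a result close to the significance boundary.

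**What to change.** In SAP 8.7, delete the 15% condition and state that the control-based pattern mixture model of SAP 9.2.8 will be run for GCA and ABC whatever the missing rate, as a supportive analysis. No separate rule is needed for baseline-only patients: the 9.2.8 code already draws every missing visit from posteriors estimated in the control arm. SAP 9.3.6 should then cite this model, not only ANCOVA-WOCF, as the check on MAR.

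Cost: one extra analysis per endpoint, using code already sketched. The primary analysis, testing order and alpha are untouched. The downsides are a possibly less favourable supportive estimate, and imprecision, because the imputation model is estimated from at most about 16 controls.
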